Two knee arthroplasty surgeons (SJM, DBC) at one hospital will perform all surgeries. Each surgeon will assess compartmental loads at three positions of knee flexion, verified by navigation data, and these measures will be repeated by the surgical assistant to ensure inter-observer reliability and consistency. The surgical technique described in Appendix 2 and 3. Data will be collected on the frequency and degree of any further adjustments required to satisfactorily balance the knee, as well as the final balance achieved. Although the surgeons will not be blinded to the allocation, the participants, assessors and statisticians will be blinded to enable unbiased collection of patient-reported outcomes and functional outcomes as secondary outcome measures.

To maintain the integrity of the trial, unblinding will occur only when knowledge of the alignment allocation is essential for further clinical management of the patient. Because both treatment arms offer current, routine standards of care, we do not anticipate this need will eventuate. If necessary however, the investigator will contact

the study coordinator to obtain the allocation assignment, and the code break will be reported in the context of Complications documentation.

Inclusion criteria

1. Patients who meet the indications for primary unilateral or bilateral total knee arthroplasty using the Smith & Nephew Legion™ posterior-stabilised total knee arthroplasty system.
2. Patients diagnosed with one or more of the following conditions:
 - Osteoarthritis
 - Rheumatoid inflammatory arthritis
 - Post-traumatic osteoarthritis

Exclusion criteria

1. Revision TKA
2. Previous insufficiency fracture
3. Prior Grade 3 ligamentous knee injury to posterolateral corner (PLC) or lateral collateral ligament (LCL). Grade 3 medial collateral ligament (MCL) injuries treated conservatively may be included so long as they were deemed by the surgeon to have healed with a maximum of Grade 1 laxity.
4. Prior femoral, tibial or patellofemoral osteotomies
5. Ipsilateral foot/ankle or hip arthritis
6. Patients who are unable to provide consent or fulfil the study requirements due to cognitive incapacity or English-language deficiency

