The surgeon will perform the initial bony resections using the same computer navigation system aiming for tibial and femoral component position perpendicular to the mechanical axis of the bone and an overall HKA of 0 degrees. These resections will be validated using the same computer navigation equipment to ensure maximum accuracy. The rest of the procedure will be completed as per the surgical technique described above.

OUTCOME MEASURES

Baseline Measures

Demographics

Baseline demographics will include age at time of surgery, gender, side of surgery, height, weight, body mass index, and primary diagnosis (osteoarthritis, rheumatoid arthritis, post-traumatic osteoarthritis).

Pre-operative Radiographic Data

Radiographic data to be recorded before surgery will include:

1. Hip-knee-ankle (HKA) angle. This is the angle subtended by the mechanical axis of the femur and mechanical axis of the tibia, with a negative value used for varus alignment and positive value for valgus alignment.
2. Lateral distal femoral angle (LDFA). This is the lateral angle subtended by the mechanical axis of the femur and a line across the distal femoral articular surface.
3. Medial proximal tibial angle (MPTA). This is the medial angle subtended by the mechanical axis of the tibia and a line across the proximal tibial articular surface.

Operative Data

Operative data to be recorded will include size of femoral component, size of tibial component, thickness of tibial bearing, size and type (oval, round onlay, inset) of patellar component, total operating time from wound incision to skin closure, intra-operative complications, VERASENSE™ data at 90, 45 and 10 degrees, and any soft tissue or bony adjustments made after the VERASENSE™ recordings.

In-Hospital Data

In-hospital data to be obtained will include total length of stay (from day of surgery to day of discharge), and discharge destination (home, in-patient rehabilitation unit, nursing home facility). Other data to be collected will include blood transfusion requirement (total number of units administered) and other in-hospital complications as specified in Table 2.

Primary Outcome Measure

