Knee Range of Motion – The patient's range of motion will be measured by a blinded orthopaedic nurse at two weeks, eight to twelve weeks and one year post-operatively. Two photographs will be taken with the patient in the supine position with markers placed on the greater trochanter, lateral epicondyle of the femur and lateral malleolus. One photograph will be taken in maximal active extension and one in maximal active flexion, with the nurse standing between 1 and 1.2m from the table to get the entire lower limb in full view and holding the camera lens level with and parallel to the patient's knee. Measurements from the photographs will be taken using computer angle measurement software. Knee flexion will be recorded as a positive value and knee hyperextension as a negative value. The following will be recorded: maximal active extension (with hyperextension as negative, full extension as zero and flexion contracture as positive); and maximal active flexion. From these two values, the arc of knee motion will be recorded (flexion minus extension).

SAMPLE SIZE

The senior authors have previously recorded the initial and final intra-compartment pressures of 280 consecutive TKAs using the VERASENSE™ device. The mean initial 10-degree pressure difference was 30psi (SD 30psi). The manufacturers recommend a pressure difference between lateral and medial compartments of <15psi in order for the knee to be balanced. Using a 5% significance, a standard deviation of 30 and an 80% power to detect a difference of 15psi, a sample size of 125 will be required. As the primary outcome measure is an intraoperative measurement, loss to follow-up will not be significant.

In addition, we aim to determine whether any differences exist in patient reported outcomes in balanced TKA's inserted with the KA or MA method. Roos and colleagues in 2003 reported a change in KOOS Pain, KOOS Symptoms and KOOS Function of 45, 37 and 41 a cohort of patients undergoing TKA [28]. The minimal clinically important change in KOOS was between 8 and 10, with a standard deviation of 16. Using a one-to-one allocation, 5% significance and 80% power to detect a 8 point change on KOOS score, a sample size of approximately 64 patients per group will be required, which would approximate the sample size of our study. [Table 2].

DATA COLLECTION AND MONITORING

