The primary outcome measure (initial pressure delta between medial and lateral compartments at 10 degrees of flexion) will be recorded intra-operatively by operating room staff in a locked and password-protected spreadsheet. The surgeon and assistant surgeon will each confirm the recorded measurement at the end of each case, and longitudinal checks for consistency and validity will be employed throughout the study.

All PROM data will be obtained from patients at pre-operative and post-operative consultations in paper form, and then stored centrally in a locked and password-protected electronic database (Socrates). Intra-operative data will be collected by members of the surgical team. In-hospital data will be collected by the trial coordinator. A CT radiographer with experience in performing post-operative alignment measures will be blinded to patient allocation, and will perform all CT-based radiographic measures.

No formal data monitoring committee is deemed necessary for this trial because of its minimal risks and because both trial arms offer standard, accepted surgical interventions. The accumulating data, however, will be monitored continuously by the principal investigator and the study monitor to determine if the trial should be modified or discontinued.

Auditing of trial conduct, including site monitoring visits, will be carried out independently by the Bellberry Limited Human Research Ethics Committee.

Stopping Rules

The trial will be terminated early if there are two (2) or more cases of tibiofemoral knee joint instability, patellofemoral instability or implant subsidence or loosening in patients assigned to the intervention arm within two years post-operatively, or if monitoring indicates a pattern of unexpected serious adverse events.

DATA ANALYSIS

The primary outcome for this study will be soft tissue balance, defined as the mean of the initial difference in pressure between the medial and lateral compartments at 10 degrees of flexion (10-degree pressure delta) measured by both the surgeon and the assistant intra-operatively immediately after the bone cuts and prior to any soft tissue correction.

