Normality of data distribution will be assessed and the Student's t-test will be used to compare differences in means with continuous variables. The Chi-squared test and Fishers exact test will be used for categorical data analysis as appropriate. Intention-to-treat analysis will be performed in the primary analysis. In addition, a per-protocol analysis including participants according to treatment received will also be added as a secondary analysis. Analysis of secondary outcomes will include mixed-model

analyses comparing secondary outcomes between time points. If greater than 20% of data is missing from the randomised sample, the missing data will be imputed. However, attempts will be made to minimise missing data by contacting patients directly by phone or via mail follow-up.

ETHICS AND DISSEMINATION

Safety considerations

Because the two groups being analysed will both be offered current routine standards of care, we do not anticipate that either the intervention or control arm will be associated with any adverse events beyond those to which patients are normally exposed during total knee arthroplasty surgery.

The trial will be conducted at St George Private Hospital (Kogarah, NSW) which has provisions for liability insurance. There will be specific information included in the Patient Information Sheet and Consent form instructing the participant to notify the principal investigators of any adverse events or complications that arise during the course of the trial.

Ethics

This study protocol was approved by the ethics committee of Bellberry Limited on 16 January 2018 (#2017-12-911) and was registered with the Australian New Zealand Clinical Trials Registry (#ACTRN12617001627347p).

Important modifications to the protocol that may impact the conduct of the study (including changes of study objectives, study design, patient population, sample sizes, study procedures or significant administrative aspects) will be communicated to Bellberry Limited and the St George Private Hospital governance board as necessary for their approval. Administrative changes of the protocol are minor corrections and/or clarifications that have no effect on the way the study is to be conducted.

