	18b	Plans to promote participant retention and complete follow-up, including list of any outcome data to be collected for participants who discontinue or deviate from intervention protocols	Specification of PRO data collection management strategies for minimising avoidable missing data. Description of process of PRO assessment for participants who discontinue or deviate from the assigned intervention protocol.	16
Data management	19	Plans for data entry, coding, security and storage, including any related processes to promote data quality (e.g. double data entry, range checks for data values). Reference to where details of data management procedures can be found, if not in the protocol		20
Statistical methods	20a	Statistical methods for analysing primary and secondary outcomes. Reference to where other details of the statistical analysis plan can be found, if not in the protocol		18
	20b	Methods for any additional analyses (e.g. subgroup and adjusted analyses)		N/A
	20c	Definition of analysis population relating to protocol non-adherence (e.g. as randomised analysis) and any statistical methods to handle missing data (e.g. multiple imputation)		18
Methods: Monitoring				
Data monitoring	21a	Composition of data monitoring committee; summary of its role and reporting structure; statement of whether it is independent from the sponsor and competing interests; reference to where further details about its charter can be found, if not in the protocol. Alternatively, an explanation of why a data monitoring committee is not needed		18
	21b	Description of any interim analyses and stopping guidelines, including who will have access to these interim results and make the final decision to terminate the trial		18
Harms	22	Plans for collecting, assessing, reporting and managing solicited and spontaneously reported adverse events and other unintended effects of trial interventions or trial conduct	State whether or not PRO data will be monitored during the study to inform the clinical care of individual trial participants, and if so, how this will be managed in a standardised way. Describe how this process will be explained to participants (e.g. in the Participant Information Sheet and Consent Form)	16, 19
Auditing	23	Frequency and procedures for auditing trial conduct, if any, and whether the process will be independent from investigators and sponsor(s).		18

Ethics and Dissemination

[figure not shown]
SPIRIT 2013 Checklist with SPIRIT-PRO Extensions

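### Free improvement: the primary comparison is an unadjusted t-test with adjusted analyses marked not applicable, although pre-operative alignment and surgeon could serve as covariates; the gain in precision is of unknown size

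*Protocol*

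**What the plan says.** The primary outcome is "the initial difference in pressure between the medial and lateral compartments at 10 degrees of flexion (10-degree pressure delta"), taken as the mean of the surgeon's and the assistant's readings before any soft tissue correction (Primary Outcome Measure; Data Analysis).

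For the comparison, Data Analysis states that the Student's "t-test will be used to compare differences in means with continuous variables", after a check of normality and by intention to treat. No covariate is named. In the SPIRIT checklist (Table 4), item 20b, "Methods for any additional analyses (e.g. subgroup and adjusted analyses"), is marked N/A, and item 20a sends the reader to the protocol's own page 18 for statistical methods.

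Under Pre-operative Radiographic Data, "Radiographic data to be recorded before surgery will include" HKA, LDFA and MPTA. The surgical plan built on these angles is fixed before randomisation (Pre-operative Templating). Study Design says that two surgeons "at one hospital will perform all surgeries". Allocation describes 1:1 permuted blocks of 4 on one list and mentions no stratification. Surgeon is not itemised among the baseline or operative data, although it is known for every case.

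The sample size section reads "Using a 5% significance, a standard deviation of 30 and an 80% power to detect a difference of 15psi", and concludes that "a sample size of 125 will be required".

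**The concern.** The protocol's theory is that a knee cut to its native anatomy will be better balanced. The mechanical alignment arm cuts perpendicular to the axis whatever the native angles are. If the theory is right, the further a patient's anatomy lies from neutral, the larger the delta should tend to be in that arm. Pre-operative alignment would then be a prognostic baseline variable that the planned test leaves unused.

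Surgeon is a second candidate. Each surgeon selects the insert, may change its thickness and replace the readings, and holds the limb by hand while the values are captured. Allocation is not described as balanced within surgeon.

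At stake is the width of the confidence interval for the primary effect and a few points of power, in a trial sized with almost no margin. Covariates chosen after the data are seen carry little weight, so the gain is available only if the model is fixed beforehand.

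**Working it through.** **Inputs.** Difference 15, SD 30, alpha 0.05, power 80%, N = 125, 1:1 (Sample Size; Table 2; Allocation). Sidedness is not stated. R², the share of outcome variance explained by surgeon and alignment, is not in the document and is varied here as an assumption.

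**1. The plan's own figure.** Per arm, n = 2(z₀.₉₇₅ + z₀.₈₀)² × SD²/difference² = 2 × (1.960 + 0.842)² × 900/225 = 62.8, so 63 per arm and 126 in total. The exact t-test gives 63.8, so 64 per arm and 128 in total. A one-sided test would need only 50 per arm. The stated 125 therefore matches a two-sided, unadjusted comparison to within rounding.

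**2. Power at 125 without covariates.** The standardised difference is 15/(30 × √(4/125)) = 15/5.367 = 2.795. The normal approximation gives Φ(2.795 − 1.960) = 79.8%; the exact t-test gives 79.2%.

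**3. Power with covariates.** Residual SD = 30 × √(1 − R²). The half-width of the 95% CI is 1.96 × residual SD × √(4/125). The equivalent unadjusted N is 125/(1 − R²).

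| Assumed R² | Residual SD | Exact power at 125 | CI half-width | Equivalent unadjusted N |
|---|---|---|---|---|
| 0 | 30.0 | 79.2% | 10.5 | 125 |
| 0.02 | 29.7 | 80.0% | 10.4 | 128 |
| 0.05 | 29.2 | 81.2% | 10.3 | 132 |
| 0.10 | 28.5 | 83.2% | 10.0 | 139 |
| 0.20 | 26.8 | 87.3% | 9.4 | 156 |
| 0.30 | 25.1 | 91.2% | 8.8 | 179 |

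Two fewer residual degrees of freedom (121 instead of 123) change these powers by less than 0.1 point.

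**4. Which R² is plausible for alignment.** Suppose alignment predicts the delta with slope b in the mechanical arm and slope 0 in the kinematic arm, with equal total variances. With 1:1 allocation, a common-slope model estimates b/2. The variance it explains is (b/2)² × Var(alignment), one quarter of what alignment explains within the mechanical arm. A pooled R² of 0.05 then needs 0.20 in that arm, 0.10 needs 0.40, and 0.20 needs 0.80. A pooled 0.30 would need 1.20, which is impossible from alignment alone. Some slope in the kinematic arm, for example where the safe zone truncates the cut, or a surgeon effect, would relax this limit.

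**5. Chance imbalance by surgeon.** Take 126 patients, 63 per arm, and one surgeon with 63 or 40 of them (assumed caseloads), using the hypergeometric distribution and ignoring the blocks. The chance that this surgeon's cases split worse than 60/40 is 3.2% or 8.4%.

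**The case against.** The strongest reply is that nothing here is wrong. An unadjusted t-test is valid under 1:1 randomisation that is not stratified by surgeon, and the sample size was worked out for that test. Both points stand. A reader might infer that the primary test is invalid or biased; the document gives no ground for that. The test's type I error already allows for chance imbalance, and no between-surgeon difference is given from which any effect of such imbalance could be sized.

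A reader might also infer that surgeon and alignment are known to drive the imbalance, so that a definite amount of precision is being thrown away. The protocol does not say so. It offers a theory and a hypothesis about alignment method, with no correlation, R² or surgeon difference. Averaging two readings also dampens some operator noise. The gain could be close to nil, and step 4 shows that the trial's own mechanism favours the lower rows of the table.

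Nor is 79% a shortfall in need of rescue. It is rounding around an 80% target, and the 132 envelopes allow for about 81% (81.4% exact).

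Finally, covariates are often left to a statistical analysis plan, which is not shown. This reply carries less weight here, because the protocol names the test, marks adjusted analyses not applicable and cites only itself for methods. Item 20b strictly concerns additional analyses, but read with the t-test sentence it describes a choice and not a gap.

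**Conclusion.** The point holds as an efficiency suggestion, not as an error. The primary comparison is fixed without covariates although baseline alignment is recorded and surgeon is known. The size of the gain cannot be derived from the document. Under assumed R² values it is about 2 points of power at 0.05, 4 at 0.10 and 8 at 0.20, and none at 0. The upper values require a strong relation in both arms or a material surgeon effect, and neither is documented. These figures assume a two-sided test, the planned SD of 30 and one observation per patient. Bilateral knees are a separate matter. Label: free improvement.

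**What to change.** Name as the primary analysis a linear model of the 10-degree delta on arm, surgeon and pre-operative alignment. Report the adjusted mean difference with its 95% CI, and keep the unadjusted t-test as supportive.

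State the form of the alignment covariate in advance. The protocol does not say whether the delta is signed or absolute, and the covariate should follow that choice: signed HKA for a signed delta, distance of HKA from neutral for an absolute one. Centre the covariate. An arm-by-alignment term is optional, and with centring the arm coefficient remains the effect at average alignment.

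Add operating surgeon as an explicit item on the data form, and amend checklist item 20b to agree with the revised text.

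The cost is about two degrees of freedom, one added data item and a short amendment to Data Analysis. No new measurement and no change in sample size is needed.

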- *EQ5D-5L* (EuroQol Research Foundation, Rotterdam, The Netherlands, <https://euroqol.org/eq-5d-instruments/eq-5d-5l-about/>) is a standard measure of overall health status that provides a simple descriptive profile and a single index value for health status. It describes five health domains: Mobility, Self-Care, Usual Activities, Pain and Discomfort and Depression. A patient indicates his or her current level of health in each of the domains: no problems, slight problems, moderate problems, severe problems or extreme problems. The patient's responses are combined in a 5-digit number describing current health state. Additionally, The EQ VAS records the respondent's self-rated health on a 20-cm vertical, visual analogue scale with endpoints labelled 'the best health you can imagine' and 'the worst health you can imagine'. This information can be used as a quantitative measure of health as judged by the individual respondents. [29, 30] The EQ5D-5L will be measured pre-operatively and at six months and two years post-operatively.
- *Satisfaction and Success – (<http://www.acornregistry.org>)* At six months and two years follow-up, patients will be asked questions related to perceived satisfaction and success. The questions are from the Arthroplasty Clinical Outcomes Registry (ACORN), to which the hospitals in this study already contribute. For satisfaction, the question asked is "*How would you describe the results of your operation?*" with five options provided: excellent; very good; good; fair; or poor. For success, the question asked

is “Overall, how are the problems now with the knee on which you had surgery, compared to before your operation?” This question also allows the person to choose one of five options: much better; a little better; about the same; a little worse; and much worse [4].

Patient-reported outcomes will be collected prior to clinical assessments, and order of administration will be standardised.

Because the primary outcome measure is recorded intra-operatively, no specific strategy for improving adherence to protocol is necessary, and there is no expected loss to follow-up for that variable.

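### The only between-arm tests the protocol names for categorical data ignore the order of the five-level satisfaction and success answers; an ordinal method on the same data would usually be more sensitive.

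*Protocol*

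**What the plan says.** Under Quality of Life Measures (Satisfaction and Success), the protocol says "At six months and two years follow-up, patients will be asked questions related to perceived satisfaction and success". The satisfaction question comes "with five options provided: excellent; very good; good; fair; or poor". The success question lets the patient "choose one of five options: much better; a little better; about the same; a little worse; and much worse". Both scales run from best to worst.

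The Data Analysis section assigns the t-test to continuous variables. For categorical data it says "The Chi-squared test and Fishers exact test will be used for categorical data analysis as appropriate". It names no outcome in that sentence. A little further on it says "Analysis of secondary outcomes will include mixed-model" analyses, described as comparisons between time points, and names neither a model type nor an outcome. Nothing states whether the five levels are kept, collapsed to two or modelled as ordered. No expected distribution, effect size or power is given for either item.

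**The concern.** On a two-by-five table, Pearson's chi-squared test and Fisher's exact test give the same p-value however the five columns are rearranged. A steady move towards the better answers therefore counts the same as a reshuffle with no clinical meaning. Neither test yields a direction or a single effect estimate. The chi-squared test also spreads its sensitivity over four degrees of freedom, when the question of interest is mostly one-dimensional: are patients in one arm better off?

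This matters because the introduction motivates the trial by the share of patients, up to 20%, who rate their knee replacement as fair or poor. The Sample Size section adds an aim of finding differences in patient-reported outcomes. With about 60 patients per arm, information on these two questions is limited, and a test that ignores order uses less of it than it could.

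**Working it through.** **1. The plan's own sample size.** The Sample Size section sets out its assumptions as "Using a 5% significance, a standard deviation of 30 and an 80% power to detect a difference of 15psi" and arrives at 125 in total. With n per arm = 2(z₀.₉₇₅ + z₀.₈₀)²·SD²/Δ²:

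2 × (1.960 + 0.842)² × 30² / 15² = 62.8 per arm, or 125.6 in total.

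The stated 125 is reproduced.

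**2. Patients available for these items.** The protocol projects no more than 5% loss for secondary outcomes: 125 × 0.95 / 2 = 59.4, so 59 per arm. Starting from the 132 prepared envelopes gives 132 × 0.95 / 2 = 62.7, so 63 per arm. Results at 63 per arm are close to those below.

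**3. Assumptions, because the protocol gives none.** Six control-arm distributions, in percent from best to worst level: four for satisfaction and two strongly skewed ones for success. The alternative is a proportional-odds shift: at every cut-point, the odds of being at that level or better are multiplied by the odds ratio (OR). Example with 40/27/15/12/6 and OR 2: the top level has odds 0.40/0.60 = 0.667; doubled, 1.333; probability 0.571. The full shifted distribution is 57.1/23.1/9.9/6.8/3.1.

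**4. Tests compared.** Pearson chi-squared, Σ(O−E)²/E on the two-by-five table, against the tie-corrected Wilcoxon-Mann-Whitney test, both two-sided at 5%. There were 20,000 simulated tables per scenario, so the simulation standard error is at most √(0.25/20,000) = 0.35 points.

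**5. Power in percent, chi-squared / Wilcoxon (gain in points, taken before rounding), 59 per arm.**

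| Assumed control distribution | OR 1.5 | OR 2 | OR 2.5 | OR 3 |
|---|---|---|---|---|
| 40/27/15/12/6 | 13 / 22 (+9) | 31 / 52 (+21) | 51 / 74 (+23) | 68 / 87 (+19) |
| 30/30/22/12/6 | 13 / 23 (+10) | 33 / 54 (+21) | 55 / 77 (+22) | 72 / 89 (+18) |
| 50/25/10/10/5 | 11 / 21 (+10) | 27 / 48 (+21) | 46 / 70 (+24) | 62 / 83 (+22) |
| 20/20/20/20/20 | 14 / 23 (+9) | 35 / 56 (+21) | 57 / 79 (+22) | 75 / 91 (+16) |
| 75/15/5/3/2 | 7 / 15 (+8) | 14 / 31 (+17) | 24 / 47 (+23) | 32 / 58 (+26) |
| 85/9/3/2/1 | 4 / 11 (+7) | 8 / 20 (+13) | 12 / 31 (+19) | 17 / 40 (+23) |

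The gain is 7 to 10 points at OR 1.5 and 13 to 26 points over OR 2 to 3.

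**6. Type I error (OR 1).** Chi-squared 2.4% to 4.9%, the low values arising with the skewed success distributions; Wilcoxon 4.7% to 5.2%. Neither is inflated.

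**7. A difference that is not a uniform shift.** The only satisfaction contrast in the protocol, in its evidence summary, is 82.1% versus 96.7% satisfied. It compares unbalanced with balanced knees, not the two alignment methods. Levels assumed to match it roughly are 35/27/20/12/6 (fair or poor 12 + 6 = 18%) against 40/32/24.7/2.5/0.8 (fair or poor 2.5 + 0.8 = 3.3%). With 59 per arm, power is 50% for the two-by-five chi-squared, 27% for Wilcoxon, and 79% for chi-squared on good-or-better versus fair-or-poor.

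**8. The dichotomy under a uniform shift.** For 40/27/15/12/6, the same two-group split has 25% power at OR 2 and 36% at OR 2.5, below both five-level tests. No single choice is best in every scenario.

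**The case against.** The strongest reply is that the protocol never says these two items will be tested this way. The sentence is general, carries a qualifier, and fits data the trial does collect: complications, discharge destination and balanced or unbalanced status. A reader might infer that the plan explicitly assigns chi-squared or Fisher to satisfaction and success. It does not. What remains is that the qualifier reads most naturally as the choice between the two named tests, neither of which uses order. The mixed-model sentence does not fill the gap, since it concerns comparisons between time points and names no ordinal model. A statistical analysis plan, not available here, may specify more, but it would have to add to or depart from this sentence.

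A second reply is that the protocol's own satisfaction figures are binary, and chi-squared or Fisher is right for a two-group split. That stands, and it is why such a split belongs in the fix. The protocol does not, however, say that the scales will be collapsed.

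A third reply concerns size. A reader might take a loss of about 20 points of power as a property of the plan. The documents do not support that: the figure depends on distributions and odds ratios they do not give, it is about half as large or less at OR 1.5, and it reverses in step 7. Nor is there a validity problem, since type I error is controlled and level percentages by arm would show the direction.

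**Conclusion.** The point holds as a low-cost improvement. The categorical tests named in the protocol do not use the order of the satisfaction and success answers, and that follows from the tests themselves without any assumption. The size does rest on assumptions: under proportional odds, with 59 per arm and the six distributions tried, an ordinal test gains roughly 7 to 10 points of power at OR 1.5 and 13 to 26 points at OR 2 to 3. If the benefit is confined largely to the fair and poor levels, the rank test can do worse than the unordered test (27% versus 50%). Both items are secondary outcomes with no power calculation of their own, and the primary conclusion on the 10-degree pressure difference does not depend on this choice.

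**What to change.** In the Data Analysis section, state that satisfaction and success will be compared between arms at six months and at two years with the Wilcoxon-Mann-Whitney test or a proportional-odds model, reporting a common odds ratio with its 95% confidence interval. Add a prespecified comparison of fair-or-poor with good-or-better satisfaction as a supportive analysis, which covers a difference concentrated in the lowest levels and prevents a cut-point being chosen after the data are seen. Keep chi-squared and Fisher's exact test for nominal and binary outcomes. The cost is a change of wording only: no new data, visits or patients.
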